4.4.2 Concomitant Medication

Partner clinics will provide all available data on medications on a monthly basis. These data should include phosphate binders, activated vitamin D, calcimimetics, and home medications.

4.5 Analysis of Primary and Secondary Endpoints

4.5.1 Analysis of the Primary Endpoint

The hierarchical endpoint of time to all-cause death followed by number of hospitalizations will be assigned a rank score using the method proposed by Finkelstein and Schoenfeld.¹

First, each patient in the trial is assigned a rank score by comparing their outcomes with the outcomes of every other patient in the trial. The comparison occurs first on mortality: the patient that survived longer is the "winner" and the other patient that died first is the "loser". The winner in the comparison has their rank score increased by 1 while the loser has their rank score reduced by 1.

In order to make this comparison appropriately, at least one of the two patients being compared had to have an observed death prior to the other patient being censored. If both patients are censored or if censoring occurred before the observed death of the comparator patient, then it cannot be determined who died first. In cases where the comparison cannot be made on death, then the patients are then compared on hospitalizations.

The comparison on hospitalizations is done through the time of the earliest censoring time of the two patients being compared. At the comparison time, the patient with fewer hospitalizations is considered the winner and the patient with more hospitalizations is considered the loser. The rank score of the winners and losers is adjusted in the same way as described above. If both patients have the same number of hospitalizations at the comparison time (including zero), then the rank score of both patients is unchanged based on the comparison.

Once a patient has been compared to all other patients in the trial, their final rank score describes their overall outcomes in comparison to the outcomes of the complete population. A higher rank score indicates the patient had better outcomes than most of the study population, while increasingly negative scores indicate worse outcomes.

To test the hypothesis of a difference between the treatment arms, the Finkelstein and Schoenfeld method will be employed. The test statistic will be

$$T = \sum_{i=1}^{N} U_i D_i$$

Where i is the participant indicator, N is the size of the analysis population, D_i is 1 in the treatment arm and 0 otherwise, and U_i is the value of the score described above.

Under the null hypothesis, the mean of T is zero and the variance is

$$V = \frac{p(N-p)}{N(N-1)} \sum_{i=1}^{N} U_i^2.$$

Here, p is the number of participants in the treatment arm. The value of T/V^{1/2} will be compared to the standard normal distribution to determine the test p-value. A p-value of less than 0.05 will indicate that there is a difference between the treatment groups.

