## 4.5 Randomization

Following consent, patients will be randomized in a 1:1 ratio to the two treatment arms. The randomization will be stratified by site in random sized blocks.

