## 8. STATISTICAL ANALYSIS PLAN AND DETERMINATION OF SAMPLE SIZE

## 8.1 Sample Size

The primary analysis of HiLo is the comparison of rank sum scores on the hierarchical composite endpoint of time to all-cause mortality and hospitalization rate. Simulations were employed to estimate the power of the planned analysis. The assumptions for the simulation include:

- 48-month study with a 24-month enrollment period
- Annual loss to follow-up rate of 5%
- 15% annual mortality rate in the standard of care arm and a hazard ratio of 0.85 comparing the intervention arm to the standard of care arm
- 35% of participants are "non-susceptible" to hospitalizations (will not have any hospitalizations during the course of the study).
- In the susceptible population, an average of 1.8 hospitalizations per year in the standard of care arm and 1.53 hospitalizations per year in the intervention arm (15% difference).

1000 different study populations with 3800 participants were simulated under the above assumptions and analyzed using the planned analysis method. The power was estimated as the percentage of significant results out of the 1000. The results of the simulation provided an estimated power above 95%. Under these same assumptions, there would be at least 80% power to detect a treatment difference for both mortality and hospitalization when analyzed as separate endpoints. These results indicate that the trial will have sufficient power to detect a treatment effect with a population size of 3800 participants.

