4. ANALYSIS METHODS

4.1 General Principles

This analysis plan is intended to support the primary and main secondary manuscripts planned for the HiLo study. Analysis plans for other manuscripts will be provided in separate documents.

In addition to specific analyses and presentations that are detailed in the following sections, results will be summarized for continuous measures using descriptive statistics, including the number of patients, mean, standard deviation, median and range as appropriate. For categorical variables, counts and percentage per treatment group will be presented. Unless otherwise specified, all statistical tests will have a two-sided significance level of α =0.05.

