4.1.1 Control of Type I Error

To account for repeated significance testing of the accumulating data, the group sequential method of Lan and DeMets will be used as a guide for interpreting interim analyses. Monitoring boundaries for the primary endpoint will be based on a two-sided symmetric O'Brien-Fleming type spending function with an overall two-sided significance level of α =0.05. The O'Brien-Fleming approach requires large critical values early in the study but relaxes (i.e., decreases) the critical value as the trial progresses. A single planned interim analysis using alpha spending will be targeted to occur after the first 2000 to 2400 subjects have been enrolled with at least 24 months of median follow up time accrued. Additional interim analyses are not currently planned but may be performed upon request by the Data Safety and Monitoring Board (DSMB).

Assuming that the interim analyses take place as currently planned with just a single analysis after ~50% of subjects have been enrolled with at least 24 months of median follow up time accrued, the critical p-value for the test of the null hypothesis of no difference at the first interim analysis will be 0.001 and a result of |z| <3 or p>0.001 would suggest that the trial should continue. In order to maintain the overall 5% significance level of the trial, the critical p-value for declaring there to be a significant difference in the primary endpoint at the final analysis will be decreased from 0.05 to 0.049. However, the critical p-values for the interim analysis can be adjusted appropriately if additional interim analyses are requested by the DSMB.

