4.5.2 Analyses of the Secondary Endpoints

The hypothesis of the main secondary endpoint of time to all-cause death will be tested in the ITT population using a Cox Proportional Hazards model including phosphate target group as an explanatory factor. The hazard ratio and 95% CI for the high phosphate target versus the low phosphate target will be calculated from the estimated model parameters. If the confidence interval does not include 1, then the null hypothesis will be rejected.

The all-cause PPY hospitalization rates will be analyzed under the following hypotheses:

H₀:
$$\mu_H = \mu_L vs. H_1: \mu_H \neq \mu_L$$

Where μ_H and μ_L are the all-cause PPY hospitalization rates in the Hi and Lo treatment arms respectively. A two-sided 95% confidence interval for the difference in the cause-specific PPY hospitalization rates between the study arms will be estimated under normality assumptions. If confidence interval does not include 0, then the null hypothesis will be rejected.

For the continuous longitudinal outcomes (change from baseline in serum albumin and PCR), mixed effect models will be created to test the null hypothesis that the change of each measure

will not differ by treatment group. The phosphate target group and the baseline measure will be included as fixed effect covariates and study site will be included as a random effect covariate in the model.

Two covariance structures for this model will be considered: the compound symmetry structure (CS) and the auto-regressive(1) (AR1) structure. Each covariance structure will be compared using the Akaike information criterion (AIC) and the Bayesian information criterion (BIC). The structure that provides better results on the AIC and the BIC will be chosen for the final adjustment model.

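### The primary test's variance ignores the site strata used in the randomization: a mild, inexpensive loss of efficiency, provided the cluster-randomized patients are outside the test

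*SAP*

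**What the plan says.** On allocation, Protocol 4.5 says: "The randomization will be stratified by site in random sized blocks". Protocol 5.3 adds that 30 units (14 Hi, 16 Lo) were enrolled under an earlier cluster design and that about 3,800 further patients will be individually randomized.

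On analysis, SAP 4.5.1 builds each score by "comparing their outcomes with the outcomes of every other patient in the trial". It sums the scores in the treatment arm to give T, and continues "Under the null hypothesis, the mean of T is zero and the variance is" V = p(N-p)/(N(N-1)) x sum of U_i^2. T/V^(1/2) is referred to the standard normal. Neither site nor stratum appears.

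In SAP 4.5.2 site enters only the albumin and PCR mixed models, where "study site will be included as a random effect covariate in the model". The Cox model for death contains phosphate target group alone, and the hospitalization-rate comparison has no site term.

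On population, SAP 2.1.1 defines ITT as everyone who consented, and SAP 1.2 speaks of 4400 patients. SAP 4.5.3 says the cluster-randomized participants may be analyzed separately and then combined with the primary analysis by meta-analysis.

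**The concern.** Blocked 1:1 allocation within each facility makes the arms nearly equal in every facility. Differences between facilities in mortality or admission practice then add almost nothing to the variance of T. The stated V still counts them, so the denominator of the test is larger than the randomization warrants. The trial takes on stratified allocation and then gives up its precision in the one test that decides its conclusion.

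The cluster cohort complicates this. There, every patient in a site has the same arm, so between-site variation adds to the variance of T in full. Whether V is too large or too small therefore depends on who is in the primary test, and the SAP does not settle that in one place.

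**Working it through.** **The plan's own figure.** Protocol 8.1 says "1000 different study populations with 3800 participants were simulated" and reports power above 95%. Its inputs are 15% annual mortality, hazard ratio 0.85, 1.8 against 1.53 admissions per year in the susceptible 65%, and 5% annual loss; censoring uniform over 2 to 4 years is taken from SAP 1.3. Simulating the SAP 4.5.1 test with these gave 98.5% (death hazard 0.15) and 99.5% (hazard -ln 0.85), 200 runs each. The protocol figure reproduces. With the SAP 1.3 admission rates (2 against 1.89), 250 runs each gave 83% and 91%. That shortfall is a separate matter, but it means spare power is not assured.

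**Why V is too large.** The scores sum to zero, so the sum of U_i^2 equals SSW + SSB, the within-site and between-site sums of squares. With equal arms and N large, V is about (SSW + SSB)/4. Under site-stratified allocation with n patients per site, the variance of T is about (1/4) x n/(n-1) x SSW. The ratio of the second to the first is about 1 - rho. In simulated null data (120 sites, blocks of 2, 4 or 6) the ratio of the two variances was 0.983, 0.969 and 0.926 where rho was 0.016, 0.031 and 0.074, as the formula predicts.

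**Type I error.** The actual two-sided level is 2(1 - Phi(1.96/sqrt(1 - rho))). The documents give no between-site variance, so rho is an assumption:

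| rho | actual level |
|---|---|
| 0 | 0.0500 |
| 0.01 | 0.0489 |
| 0.02 | 0.0477 |
| 0.05 | 0.0443 |
| 0.10 | 0.0388 |

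Re-randomizing null data within site gave:

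- 120 sites, lognormal site effects, 4,800 allocations per scenario (Monte Carlo SE about 0.003). With no site effect the level was 0.049 for both variances. At rho 0.016, 0.031 and 0.074 it was 0.044, 0.046 and 0.041 as written, against 0.045, 0.049 and 0.050 with the stratified variance.
- 125 sites of 30, SAP 1.3 inputs, one site effect shared by death and admissions with SD 0.2, 0.3 and 0.4. Rho was about 0.03, 0.07 and 0.10. A run of 4,500 allocations gave 5.1%, 4.5% and 4.1% as written, and 5.0% to 5.4% stratified. A run of 20,000 gave 4.8%, 4.1% and 3.4% as written, and 5.0%, 5.0% and 4.95% stratified.
- If the site effect acts on admissions only, rho falls to 0.004 to 0.02 over the same SDs.

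**Power at site SD 0.3, as written against stratified.**

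- Protocol effects, 150 trials: 98.0% against 98.7%; mean z 4.06 against 4.13.
- SAP effects, 250 trials: 82.4% against 84.0%; mean z 2.87 against 2.96. Another 198 trials gave 79% against 81%; mean z 2.63 against 2.72.

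The theoretical gain in z is 1/sqrt(1 - rho): 1.016 at rho 0.031 and 1.037 at rho 0.07. The observed ratios are 4.126/4.063 = 1.015 and 2.96/2.87 = 1.031. At SD 0.4 with SAP effects, 250 trials gave 80.4% against 84.4%. In sample-size terms the gain is about rho x 3800: 76 patients at rho 0.02 and 190 at rho 0.05.

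**If the cluster cohort is pooled.** It has about 4400 - 3800 = 600 patients in 30 sites, so 20 per site. Relative to V, the true variance is about (3800/4400)(1 - rho) + (600/4400)(1 + 19 rho) = 1 + 1.73 rho. At rho 0.02 this is 1.035, giving a level of 2(1 - Phi(1.96/sqrt(1.035))) = 0.054. At rho 0.05 it is 1.086, giving 0.060.

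**The case against.** The strongest reply is that, for the individually randomized cohort, validity is intact. An unadjusted primary test that errs slightly on the safe side is a legitimate choice, and under the protocol's effects the gain is less than a point of power. This stands, and it is why the point is an improvement and not a correction of an error.

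The size also rests entirely on assumed site variation. An SD of 0.3 implies that the central 95% of facilities span exp(2 x 1.96 x 0.3) = 3.2-fold in true rates on both outcomes; an SD of 0.4 implies 4.8-fold. Nothing in the documents supports values that large, and sharing one effect across both outcomes raises rho. This stands too: the 3.4% result belongs to the most extreme assumption, and the shorter run at the same SD gave 4.1%.

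A reader might infer that the SAP models site everywhere except in the primary test. It does not: the Cox and hospitalization-rate analyses omit site as well, so the primary and both main secondary analyses are uniformly unadjusted.

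A reader might also infer that every primary p-value will be too large. That does not follow. The stratified version re-centres T as well as shrinking V, so a single result can move either way; in one run of 40 trials under SAP effects the stratified z was smaller in 2.

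**Conclusion.** The mismatch between allocation and variance is plain in the text, and its direction follows from algebra for the individually randomized cohort. The test as written is mildly conservative on average: about 4.9% to 3.9% at nominal 5% for rho from 0.01 to 0.10. At a site SD of 0.3 the matching variance gains under 1 point to about 2 points of power, and almost nothing changes if sites do not differ. These sizes assume 120 to 125 equal sites, blocks of 2 to 6 and lognormal site effects, none of which the documents specify beyond 100 to 150 facilities and random-sized blocks.

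A reader might take the primary test to be conservative without condition. The documents do not support that. SAP 4.5.3 implies that the cluster cohort lies outside the primary test, while SAP 2.1.1 and 1.2 read as if it were inside. If it is inside, V is too small and the level is about 5.4% to 6.0% for rho of 0.02 to 0.05.

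The significance threshold does not affect the conclusion. SAP 4.5.1 uses 0.05, while SAP 4.1.1 says the final critical value "will be decreased from 0.05 to 0.049". At rho 0.05 the actual level is 0.0443 with the former and 0.0434 with the latter.

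**What to change.** 1. State in SAP 2.1.1 and 4.5.1 that the primary test, including the pairwise scoring, is restricted to individually randomized patients, with the cluster cohort handled separately as SAP 4.5.3 describes. This matters for the formula below as well: in a single-arm site both p_s(n_s - p_s) and the contribution to T - E(T) are zero, so pooled cluster patients would silently drop out of the statistic.
2. Keep the all-pairs scores U_i, so that no comparisons are lost, and replace the moments of T. With p_s of n_s patients in site s on the treatment arm:
   - E(T) = sum over s of p_s x mean(U in s)
   - V = sum over s of [p_s(n_s - p_s)/(n_s(n_s - 1))] x sum over i in s of (U_i - mean(U in s))^2
   - refer (T - E(T))/V^(1/2) to the standard normal.

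   This approximates the allocation, because it conditions on site totals and ignores the blocks within site.
3. Fix a rule for very small sites before unblinding. A one-arm site contributes nothing, and a single-patient site makes the formula 0/0. Set such terms to zero or pool very small sites.

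The cost is one formula, one sentence on the population and a few lines of code. Site is already recorded. If the sponsor prefers the unstratified variance, the SAP should say that it is a deliberate conservative choice; item 1 is needed either way.

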4.5.2 Analyses of the Secondary Endpoints

The hypothesis of the main secondary endpoint of time to all-cause death will be tested in the ITT population using a Cox Proportional Hazards model including phosphate target group as an explanatory factor. The hazard ratio and 95% CI for the high phosphate target versus the low phosphate target will be calculated from the estimated model parameters. If the confidence interval does not include 1, then the null hypothesis will be rejected.

The all-cause PPY hospitalization rates will be analyzed under the following hypotheses:

H₀:
$$\mu_H = \mu_L vs. H_1: \mu_H \neq \mu_L$$

Where μ_H and μ_L are the all-cause PPY hospitalization rates in the Hi and Lo treatment arms respectively. A two-sided 95% confidence interval for the difference in the cause-specific PPY hospitalization rates between the study arms will be estimated under normality assumptions. If confidence interval does not include 0, then the null hypothesis will be rejected.

For the continuous longitudinal outcomes (change from baseline in serum albumin and PCR), mixed effect models will be created to test the null hypothesis that the change of each measure

will not differ by treatment group. The phosphate target group and the baseline measure will be included as fixed effect covariates and study site will be included as a random effect covariate in the model.

Two covariance structures for this model will be considered: the compound symmetry structure (CS) and the auto-regressive(1) (AR1) structure. Each covariance structure will be compared using the Akaike information criterion (AIC) and the Bayesian information criterion (BIC). The structure that provides better results on the AIC and the BIC will be chosen for the final adjustment model.

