4.5.3 Additional Analyses

An adjusted analysis of the main secondary endpoints will be performed. The following adjustment variables will be included in the models:

- Age
- Sex
- Race
- Calculated BMI
- Cause of end-stage renal disease
- Vascular access type

The covariance structure for the model will be selected in the same manner as for the serum albumin and PCR analyses described in section 4.5.2.

An adjusted analysis of time to all-cause death will be performed by repeating the analysis of the endpoint described in section 4.5.2, but including the same adjustment variables listed for the adjusted analysis of the primary endpoint in the Cox model.

Similarly, the analyses for the serum albumin and PCR will be repeated including the same adjustment variables in their respective models.

The ratio of hospitalized days will be tested with the following hypotheses:

 $H_0: \mu_H = \mu_L vs. H_1: \mu_H \neq \mu_L$

Where μ_H and μ_L are the mean ratio of hospitalized days in the Hi and Lo treatment arms respectively. If the two-sided 95% confidence interval for the difference in the mean ratios does not include 0, then the null hypothesis will be rejected.

Under a previous HiLo protocol, cluster randomization at the site level occurred but otherwise participants were enrolled and participated in the study in a similar manner to the current protocol. If it is determined to be appropriate, the primary outcomes of the participants enrolled under the cluster randomization will be analyzed separately. Furthermore, the results of this analysis will be combined with the primary analysis detailed in this SAP using meta-analysis methods. Details of both the analysis of the cluster randomized data and the meta-analysis will be provided in a future version of this document.

Additional analyses concerning COVID-19

Additional analyses are planned to investigate and control for the potential effect of the COVID-19 outbreak on the other planned analyses. If the data are available to construct an endpoint as described in section 3.3, then the primary and secondary analyses will be repeated using only non-COVID-19 related deaths and hospitalizations as endpoint events. Patients experiencing a death attributed to COVID-19 will be censored at the time of death.

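### The deciding mortality test is a Cox model with arm alone, which leaves unused the power that the already planned covariate-adjusted model would offer

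*SAP*

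**What the plan says.** SAP 4.5.2 tests the main secondary endpoint, time to all-cause death, in the ITT population "using a Cox Proportional Hazards model including phosphate target group as an explanatory factor". The decision rule is: "If the confidence interval does not include 1, then the null hypothesis will be rejected". No covariate or site term is named.

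SAP 4.5.3 then states: "An adjusted analysis of the main secondary endpoints will be performed". It lists age, sex, race, BMI, cause of ESRD and vascular access, and says the Cox model for death will be repeated with these variables. That model carries no decision.

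Protocol 5.4 draws demographics, height, weight, dialysis vintage, comorbidity and cause of ESRD at entry, and access type and albumin monthly, from routine records for all participants. SAP 5.3 allows no imputation except for dates.

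Protocol 8.1 claims power above 95% for the hierarchical composite, but only "at least 80% power to detect a treatment difference" for mortality and hospitalization taken separately.

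**The concern.** In a Cox model, omitting baseline variables that predict death moves the treatment hazard ratio toward 1 relative to its covariate-conditional value and weakens the test. The plan makes the less powerful of its two mortality models the deciding one, although the covariates come from routine data and need no new collection.

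This matters more for death than for the composite because the mortality claim sits at or just above 80%. At stake is the chance of detecting a real mortality difference. The type I error of the test is not in question.

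**Working it through.** **1. Reproduce the stated power.** Inputs: 3800 participants (Protocol 8.1: "1000 different study populations with 3800 participants were simulated under the above assumptions"); 1:1 allocation (Protocol 4.5), so 1900 per arm; "15% annual mortality rate in the standard of care arm and a hazard ratio of 0.85" and 5% annual loss (Protocol 8.1); administrative censoring uniform over 2 to 4 years (SAP 1.3); two-sided 0.05 (SAP 4.1).

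With death hazard h, loss hazard c and k = h + c, expected deaths per arm are

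1900 × (h/k) × {1 − [exp(−2k) − exp(−4k)]/(2k)}.

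Power is Φ(√D × |ln 0.85|/2 − 1.96), where D is total deaths and |ln 0.85| = 0.1625.

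- 15% and 5% read as hazards. Lo: 1900 × 0.750 × (1 − 0.5525) = 638. Hi (h = 0.1275): 1900 × 0.7183 × (1 − 0.5902) = 559. D = 1197; power = Φ(2.811 − 1.96) = 80.3%.
- Read as annual probabilities (h = −ln 0.85 = 0.1625, c = −ln 0.95 = 0.0513). Lo 678, Hi 596. D = 1274; power = Φ(2.900 − 1.96) = 82.6%.

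Freedman's formula gives 80.1% and 82.5%. The protocol's claim is reproduced.

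**2. Slack.** Deaths needed for 80% power: 4 × (1.96 + 0.842)²/0.1625² = 1189. The margin is 1197 − 1189 = 8 to 1274 − 1189 = 85 deaths. In each pair below, the first figure reads the rates as hazards and the second as annual probabilities:

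- Follow-up of 27 to 45 months (Protocol 4.4): 80.4% and 82.8%.
- Follow-up of 21 to 45 months (45-month duration less 24-month enrollment, synopsis): 77.6% and 80.2%.
- SAP 1.3 rates of 15% versus 12.8%: 78.4% and 86.2%.
- Total censoring of 10% a year (assumed): 77.5% and 79.8%.

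**3. Gain from adjustment.** The documents give no prognostic strength, so it is varied. Simulation: 1500 trials per row, N = 3800, annual-probability reading, and one standard-normal prognostic score with log-hazard SD σ. Each simulated trial is analyzed with arm alone and with arm plus score. Monte Carlo SE is about 1 point.

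| σ (assumed) | 0.85 marginal: unadjusted → adjusted | 0.85 conditional: unadjusted → adjusted |
|---|---|---|
| 0.3 | 83.8% → 85.0% | 82.8% → 83.9% |
| 0.5 | 81.9% → 84.5% | 78.2% → 82.3% |
| 0.7 | 81.9% → 87.3% | 74.5% → 81.5% |
| 0.9 | 78.3% → 90.1% | 66.9% → 81.1% |

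With σ = 0 nothing is gained or lost (83.3% against 83.5%). The two columns differ because a conditional HR of 0.85 corresponds to a marginal HR of 0.852, 0.855, 0.861 and 0.869 for the four values of σ.

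**4. Adding site stratification.** Power for unadjusted / adjusted / adjusted and stratified, with 125 sites (mid-range of 100-150), conditional HR 0.85, no site heterogeneity and 600 trials per row:

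- σ = 0.3: 82 / 84 / 82%
- σ = 0.5: 78 / 82 / 81%
- σ = 0.7: 73 / 82 / 79%

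At 125 sites there are about 3800/125 ≈ 30 patients and 1197/125 ≈ 10 deaths per stratum, so information is lost within strata. A further set of 1000 trials per row, with an assumed site log-hazard SD of 0.2, gave 80.2 / 81.1 / 81.5%, 76.0 / 81.0 / 80.1% and 71.1 / 79.4 / 77.0% for the same σ values. Modest site heterogeneity therefore does not reliably restore what stratification costs.

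**The case against.** The unadjusted test is valid under randomization, drops nobody for missing covariates and estimates a marginal hazard ratio that is easy to explain. Protocol 8.4 asks only for standard Cox methods. Mortality is a secondary endpoint, the primary test has stated power above 95%, and the adjusted estimate will be reported anyway. All of this stands. It makes the point one of efficiency, but it gives no reason to let the weaker of two prespecified models decide.

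A reader might infer that the planned test really has only 67% to 78% power. That needs 0.85 to be a covariate-conditional hazard ratio and the covariates to have an SD of 0.5 or more. Protocol 8.1 and SAP 1.3 describe mortality by arm and mention no covariates, so the marginal reading is the natural one. On it, unadjusted power is 78% to 84%.

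A reader might also infer that the covariates are known to be strong. The documents do not quantify them, and at σ = 0.3 the gain is about 1 point.

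Finally, because randomization is stratified by site, full site stratification of the Cox model may look like part of the remedy. In most of the scenarios simulated it gives back part of the gain.

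**Conclusion.** The point holds as a moderate, inexpensive improvement on a main secondary endpoint. Stated mortality power is reproduced at 80.3% to 82.6%, a thin margin over 80%. Making the adjusted model decisive adds about 1, 3, 5 or 12 points (marginal 0.85) or 1, 4, 7 or 14 points (conditional 0.85) for assumed σ of 0.3, 0.5, 0.7 or 0.9. The direction is the same on both readings; the size rests on the assumed σ.

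These figures represent the covariates by a single fully observed score. Missing covariates handled by complete-case analysis would erode the gain. Counting all 4400 participants would give unadjusted power of 85.7% to 87.7%, but SAP 4.5.3 sets the cluster-phase participants aside for a separate analysis. Nothing here supports calling the unadjusted test biased under the null or invalid.

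**What to change.** - In SAP 4.5.2, make the Cox model adjusted for the SAP 4.5.3 list the deciding mortality test. Dialysis vintage and baseline albumin, both collected, may be added. Report the unadjusted hazard ratio as supportive.
- Fix the list and the form of each covariate before unblinded data are seen. State that access type and albumin, which are recorded monthly, enter at their baseline value.
- Correct the cross-reference in SAP 4.5.3: the Cox paragraph points to an adjusted analysis of the primary endpoint, while the list is introduced for the main secondary endpoints.
- Add an exception to SAP 5.3 allowing a missing category or simple single imputation for baseline covariates, so that no randomized patient is dropped.
- Do not require stratification by 100-150 sites. If site is to be reflected, use a site random effect (frailty) as a sensitivity analysis.

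The cost is SAP wording, some specification of covariates and their missing values, and the programming that goes with it; the documents do not show that the adjusted model has been programmed. The main downside is that the headline hazard ratio becomes conditional on the covariates, which the report should say.
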